Pro00107657: A self-directed mobile mindfulness intervention to address distress and burnout in frontline healthcare workers.

Version Date: v1.0 - 3/31/2021

NCT04816708

Clinical Protocol Synopsis

1. Title

A self-directed mobile mindfulness intervention to address distress and burnout in frontline healthcare workers.

2. Background

Emotional distress and burnout are common amongst U.S. health care workers^{1,2}. In nurses specifically, observational studies have estimated the rate of burnout to be as high as 50%⁽³⁾. Nurses are also more likely than the general population to report insomnia, depressive symptoms, and anxiety⁴⁻⁸. The onset of the COVID-19 pandemic has led to increased physical and psychological demands on frontline healthcare workers, as they have been asked to work more hours with an increased risk to their own personal health and safety^{9,10}.

Mindfulness is a type of mind-body therapy that promotes a practice of non-judgmental awareness that can alleviate distress by uncoupling emotional reactions and habitual behavior from unpleasant symptoms, thoughts, and emotions. LIFT is a mobile app which can assess levels of emotional distress via survey, and subsequently offer mindfulness content that has previously been used in ICU patients, where it was shown to reduce symptoms of depression, anxiety, and PTSD¹¹.

3. Focus of the Study and Specific Aims.

LIFT-HC is a pilot randomized waitlist control trial (RCT) that tests the efficacy of the LIFT mobile app in relieving symptoms of emotional distress amongst nurses directly caring for COVID-19 patients in the Duke University Health System.

AIM 1: To determine the feasibility of using the LIFT app among nurses directly caring for COVID-19 patients. *Hypothesis: Nurses taking care of COVID-19 patients will have high levels of Lift app use and low levels of dropout over the course of 1 month follow up.* Data collected by the app will inform the study team as to the frequency of use and compliance among participants randomized to receive mobile mindfulness content. Participants will be allowed to comment on usability of app and features that they thought worked well and did not work well. A subset of participants randomized to intervention with high app usage and a subset with low app usage will be approached to complete a telephone interview to comment on usability and areas for improvement in the app.

AIM 2: To assess the clinical impact of LIFT compared to control among nurses directly caring for COVID-19 patients at 1 month. *Hypothesis: Nurses using the LIFT app's mindfulness content will have reduced levels of emotional distress compared to usual care.* After completion of baseline studies, 100 nurses will be randomized in a 2:1 fashion to LIFT (intervention) or waitlist (control). Levels of emotional distress for all participants in both arms will be reassessed after 30 days via questionnaire completion. Surveys will assess anxiety (GAD-7), depression (PHQ-9), burnout (MBI), stress (PSS-4) as well as self-reported job performance quality and medical errors.

Pro00107657: A self-directed mobile mindfulness intervention to address distress and burnout in frontline healthcare workers.

Version Date: v1.0 - 3/31/2021

NCT04816708

4. Study Population

This study will enroll nurses working primarily in units where they take direct care of patients with COVID-19.

Inclusion Criteria:

1. Adult \geq 18 years of age
2. Currently working as a nurse primarily in an adult COVID unit at Duke University Hospital
3. English Fluency

Exclusion Criteria

1. Lack of access to either reliable smartphone with cellular data plan or home internet access.
2. Anticipation of leaving current position in \leq 30 days.

5. Screening and Recruitment

No active screening to identify potential participants will take place. The study team will use e-mail and flyers as the main way to recruit participants. There will also be an in-person introduction to the study at nursing huddles, but this will direct potential participants to e-mail or flyers to enroll in the study if they wish to proceed. The IRB approved e-mail will contain a hyperlink to a website (<https://lift.duke.edu/nurse/>) that describes the study's purpose, duration, and risks and benefits. The e-mail/flyer will also contain a link to a video explaining the LIFT app and mindfulness therapy.

If a participant wishes to enroll, then they will be directed via hyperlinks in the e-mail or QR code in the flyer to download the generic Pattern Health mobile app platform from either the Google App store (for Android phones) or the Apple App store (for Apple phones). Both the e-mail and the flyer will contain contact information for the study PI, [name], so that all questions can be answered prior to consent.

6. Process of obtaining informed consent

Prior to conduct of study procedures, informed consent will be obtained from all participants.

Consent will be obtained through Pattern Health app. After downloading the generic Pattern Health app as outlined in section 5., participants will enter the registration code "NURSE" contained in e-mail/flyer. This will then initiate the in-app self-guided consent process where participants sign an IRB-approved informed consent document electronically. A copy of the consent for each participant

Pro00107657: A self-directed mobile mindfulness intervention to address distress and burnout in frontline healthcare workers.

Version Date: v1.0 - 3/31/2021

NCT04816708

will be saved within the Pattern Health server, and will be available for each participant via the app. On a monthly basis, a copy of the consents will be exported into secure, Duke University-approved, password protected, cloud systems (i.e., Box) for long term storage.

7. Data collection

All data will be collected via the LIFT app. Each participant, regardless of randomization arm, will be asked to complete the following surveys at the listed time points below:

- Baseline (upon app registration and randomization); T1
 - Baseline sociodemographic data
 - GAD-7, PHQ-9, MBI, and PSS-4
 - Single item questions regarding impact of COVID-19 on mental health
 - Single item questions regarding perceived job performance and medical errors
- T2 (30 days post-enrollment)
 - GAD-7, PHQ-9, MBI and PSS4
 - Single item questions regarding perceived job performance and medical errors

Participants randomized to the intervention arm will also be asked to complete the following:

- T2 (30 days post-enrollment)
 - An open-ended narrative question commenting on usability of the app

8. Randomization

Randomization will happen via the LIFT app. After completion of the in-app consent process, as well as a baseline demographic survey, participants will be randomized in a 2:1 fashion to intervention vs. waitlist (control). Randomization will be stratified based on baseline PHQ-9 scores and years of experience as a nurse.

9. LIFT-Healthcare Worker procedures.

This is a single site, pilot randomized waitlist control trial exploring feasibility of use and clinical impact of the LIFT app amongst nurses directly caring for COVID-19 patients. We aim to enroll 100 participants. Nurses agreeing to participate will be asked to download and register the LIFT app on their mobile device. Consent will be provided electronically through the LIFT app. After signing consent, participants will be randomized via the LIFT app in a 2:1 fashion into two arms:

Pro00107657: A self-directed mobile mindfulness intervention to address distress and burnout in frontline healthcare workers.

Version Date: v1.0 - 3/31/2021

NCT04816708

- Arm 1: Intervention group (access to LIFT mindfulness content)
- Arm 2: Waitlist (delayed access to LIFT content)

LIFT is a self-directed mobile app platform based on a solid conceptual model that guides participants through a 1-month program. LIFT content includes 4 weekly app-based sessions as previously tested in a pilot RCT (NCT02701361). Each session is composed of three parts: 1. Video presentation describing rationale (3-5 min.), 2. Audio guided meditation (8-10 min.), and 3. Other relevant in-app exercises (e.g., tips to help apply mindfulness to daily life). The app-based approach to non-responders, defined as those whose PHQ-9 score has increased in comparison to the previous week or whose PHQ-9 score is ≥ 20 , uses the app's logic to display hovering messages and notifications within the app that may be applicable to the user. Depending on whether emotional or somatic depression symptoms are dominating the PHQ-9 score for the individual, a unique video is shown within the app that features the study interventionists leading a brief exercise in which the participant is coached by the interventionist in the application of mindfulness for the symptoms the participant has endorsed. The app-based approach to non-responders has 8 unique videos, 2 for each week (i.e., one tailored to emotional symptoms, one tailored to somatic symptoms).

AIM 1, which is to determine the feasibility of using the LIFT app among nurses directly caring for COVID-19 patients, will be assessed via the app which tracks user fidelity and adherence, and the use of an interactive dashboard for administrative users (i.e., study team) to track individual participant use. The open-ended narrative question at T2 will also help provide guidance for improving usability in future studies, as will directed telephone interviews with participants with high and low app usage as outlined above.

AIM 2, which is to assess the clinical impact of LIFT compared to control among nurses directly caring for COVID-19 patients at 1 month, will be assessed by comparing changes from in the GAD-7, PHQ-9, MBI-7, and PSS-4 over the study duration between intervention and waitlist groups.

10. Statistical design, analyses, sample size, and power

Statistical Design and Analyses Plan

The primary goal of this pilot RCT is to explore the feasibility and impact of the LIFT app in healthcare workers to inform a definitive future clinical trial. To do so, we will test differences between observed and a priori defined benchmarks among LIFT recipients using t-tests for continuous variables and chi-square tests for categorical variables.

The secondary goal is to estimate a reasonable range of clinical effect of LIFT in comparison to a usual care control condition. General linear models will be used to estimate mean changes and corresponding 95% confidence intervals (CIs) in psychological distress (i.e., GAD-7, PHQ-9) for each treatment group over the 1-month study period using SAS PROC MIXED (SAS Institute, Cary NC). We will fit the models with an unstructured covariance matrix to better understand and represent the correlation between repeated measures.

Pro00107657: A self-directed mobile mindfulness intervention to address distress and burnout in frontline healthcare workers.

Version Date: v1.0 - 3/31/2021

NCT04816708

Participants with low baseline levels of emotional distress, as indicated by a PHQ-9<5, will not be excluded from participating in the study, but we do not plan to use them in the primary analysis.

Sample Size and Power

This exploratory trial is not intended to test LIFT efficacy. While the 100-person sample size reflects the pragmatics of recruitment during a short enrollment period, it is large enough both to inform us about feasibility of use as well as to provide meaningful confidence intervals for our estimates as was true for the similarly sized LIFT pilot RCT.

11. Subject Participation and Duration

It will require 1 month (30 days) for participants to complete the entire study, from the time of randomization to completion of T2 surveys.

12. Study Duration

We estimate that from the time the RCT opens to enrollment it will require 1 year to complete all study activities.

13. Costs to the Subject

There are no costs to participants.

14. Compensation

Participants will receive a \$10 gift-card for completion of the study.

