There are several ongoing mechanisms for monitoring the occurrence of adverse events. The investigators will perform day-to-day monitoring of the study. This research team has demonstrated in research involving nearly 1,500 participants to date that they can keep careful records of participants study engagement and wellbeing. Careful monitoring of all persons entering the study will minimize attrition and will ensure the clinical safety. This monitoring is facilitated by a telephone number (PI's cell phone) and email address (PI's e-mail address) provided to participants upon entry into the study to report concerns related to study participation, weekly meetings between the clinical research coordinators and co-investigators to discuss study progress and any adverse events, and direct supervision of the study by the PIs.

Plans to prevent coercion and to ensure voluntary participation

We will strive to create an environment free of any coercive practices for participants. We will stress that study involvement is absolutely voluntary and that choosing to participate or not participate will not affect their employment in any way. [name] will not be involved in any recruitment activities in the medical ICU, as he holds a clinical leadership position in that unit, so as to avoid the appearance of coercion. No nursing managers will be involved in recruitment either, also to avoid the appearance of coercion.

Vulnerable populations. We will not enroll participants from vulnerable populations (e.g., imprisoned persons, minors).

17. Data & safety monitoring

Data Accuracy and Protocol Compliance.

The PI will supervise the study, including data management, data accuracy, and protocol compliance. The PI will be the chief data manager and will adhere to established federal and institutional safety and protection guidelines. To assure data accuracy, the PI will review data system reports on a routine basis. These reports will show enrollment, missing data, and other values that are neither study ID- nor outcome-based.

Quality Assurance

First, the electronic data entry system "forces" responses to key questionnaire items (e.g., baseline demographics and surveys) before allowing progression to treatment arm randomization and access to app content, thereby minimizing missing data at timepoint 1.

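### Aim 2 compares changes between arms with no stated baseline adjustment; if T1 means are free by arm, the LIFT-minus-waitlist interval is modestly wider than it need be

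*Combined protocol and SAP*

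**What the plan says.** Section 9 says that Aim 2 "will be assessed by comparing changes from in the GAD-7, PHQ-9, MBI-7, and PSS-4 over the study duration between intervention and waitlist groups". Section 10 sets the purpose: "The secondary goal is to estimate a reasonable range of clinical effect of LIFT in comparison to a usual care control condition". The method is then given: "General linear models will be used to estimate mean changes and corresponding 95% confidence intervals (CIs) in psychological distress", for GAD-7 and PHQ-9, by treatment group, in SAS PROC MIXED. On covariance it adds: "We will fit the models with an unstructured covariance matrix to better understand and represent the correlation between repeated measures".

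Four other statements bear on the point.

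- Section 8: "Randomization will be stratified based on baseline PHQ-9 scores and years of experience as a nurse". Neither factor reappears as a model term.
- Section 10, on participants with baseline PHQ-9 below 5: "we do not plan to use them in the primary analysis".
- Section 10, Sample Size and Power: the 100 participants, randomised 2:1, are said to be enough "to provide meaningful confidence intervals for our estimates".
- Section 17, Quality Assurance: key baseline items are forced "before allowing progression to treatment arm randomization and access to app content, thereby minimizing missing data at timepoint 1".

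Nowhere do the documents say whether the T1 means are free by arm or held equal, or whether the T1 score is a covariate.

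**The concern.** An unstructured covariance matrix does not by itself adjust for baseline. With two time points, complete data and a separate T1 mean for each arm, the arm-by-time contrast is exactly the raw difference in mean change. A change score takes off the whole baseline value, whereas regression takes off only the part that predicts T2. The change-score contrast is therefore in general the less precise of the two.

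The trial makes no efficacy claim, so the between-arm interval is the main product of Aim 2 and an input to the future trial. There are only about 33 controls, and fewer if those with PHQ-9 below 5 are left out. The adjusting variable is already collected and should be nearly complete. Separately, stratifying on a factor and then leaving it out of the model tends to give an interval wider than the design has earned.

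**Working it through.** **Inputs.** From the documents: N = 100 at 2:1 (about 67 and 33), one follow-up at 30 days, 95% intervals, and stratification on baseline PHQ-9 and years of experience. Assumed, because the documents give none: T1–T2 correlation r of 0.5, 0.7 and 0.85; SD of 1 at both times unless stated; fraction d missing T2; T1 variance v in the analysed set (1 in the whole sample); and 40/20 as the size of the set with PHQ-9 of 5 or more. The plan states no interval width, so there is no figure to reproduce.

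**Step 1. Equivalence.** In 300 simulated 67:33 trials with complete data, the unstructured model with free T1 means matched the raw difference in mean change (largest discrepancy 4e-15). At r = 0.6 its standard error was 0.188, against 0.168 with T1 means held equal. That ratio is 1.12; theory, sqrt(2/(1 + r)), gives 1.118.

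**Step 2. Half-widths, whole sample, complete data.**

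- Free T1 means: t(98) × sqrt[2(1 − r)(1/67 + 1/33)].
- Adjusted: t(97) × sqrt[(1 − r²)(1 + 1/96)(1/67 + 1/33)].
- Results, free then adjusted: 0.42 and 0.37 SD (r = 0.5); 0.33 and 0.30 (r = 0.7); 0.23 and 0.22 (r = 0.85).

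**Step 3. Narrowing of the reported interval.** Write T2 = r·T1 + e. The free-means variance is proportional to (1 − r²) + (1 − r)²·v·(1 − d), and the adjusted variance to (1 − r²). Narrowing is 1 − sqrt(adjusted/free). For example, with r = 0.5, v = 1 and d = 0: 1 − sqrt(0.75/1.00) = 13.4%.

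| Set | d | r = 0.5 | r = 0.7 | r = 0.85 |
|---|---|---|---|---|
| Whole sample, v = 1 | 0 | 13.4% | 7.8% | 3.8% |
| Whole sample, v = 1 | 0.2 | 11.1% | 6.4% | 3.1% |
| PHQ-9 ≥ 5, v = 0.85 | 0 | 11.7% | 6.7% | 3.3% |
| PHQ-9 ≥ 5, v = 0.85 | 0.2 | 9.7% | 5.5% | 2.6% |
| PHQ-9 ≥ 5, v = 0.5 | 0 | 7.4% | 4.1% | 2.0% |
| PHQ-9 ≥ 5, v = 0.5 | 0.2 | 6.1% | 3.4% | 1.6% |

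The PHQ-9 ≥ 5 rows are for PHQ-9 itself. A v of 0.85 fits skewed scores cut at 5; a v of 0.5 is close to a normal score cut at −0.4 SD (0.46).

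**Step 4. Unequal SDs.** Let k be the T2/T1 SD ratio (whole sample, complete data). Narrowing is 1 − sqrt[k²(1 − r²)/(1 + k² − 2rk)]. At k = 1.2 it is 6.7%, 1.7% and 0.1%; at k = 0.8 it is 24.4%, 20.8% and 20.4%.

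**Step 5. True precision under stratified randomisation.** Steps 2 to 4 describe the reported width. The real sampling spread was simulated with 2:1 blocks of 3 within strata. The PHQ-9 cut-points are assumed, because the plan gives none.

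- PHQ-9, N = 99, median split: true gain about 4% to 6% at r = 0.5 across separate runs, about 3% at r = 0.7 and 1.5% at r = 0.85.
- PHQ-9, N = 99, four strata: 2.4%, 1.3% and 0.7%.
- PHQ-9, N = 60, truncated baseline, median split: 2.2%, 1.6% and 0.5%.
- Reported PHQ-9 half-widths at r = 0.5, N = 99, median split: still 0.422 unadjusted against 0.366 adjusted. The unadjusted 95% interval covered 96.7% of the time.
- An outcome such as GAD-7, r = 0.5, baseline correlating 0.6 with PHQ-9 (assumed): empirical SDs 0.208 and 0.183, a true gain of 1 − 0.183/0.208 = 12%. With a correlation of 0.7, the gains are 9.4%, 5.1% and 2.3% at the three values of r.

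**Step 6. Cost of the extra terms.** At 40/20 under stratified allocation, factors unrelated to the outcome widen the interval by 0.4% (one) or 0.8% (two).

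**The case against.** The strongest reply is that the plan does not commit to the less efficient model. A PROC MIXED repeated-measures model can be fitted with T1 means free or equal, and comparing changes between arms fits both. This stands: the point is conditional, and the loss is zero if a common T1 mean is intended. A reader might infer that the plan has chosen a change-score analysis, but the text does not say so.

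A reader might also take 13% as a loss of precision on every outcome. The documents do not support that. The figure is for the whole sample, while participants with PHQ-9 below 5 are outside the primary analysis, and stratification on baseline PHQ-9 already supplies most of the true gain for that scale.

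It can fairly be added that the half-widths differ by only 0.05, 0.03 and 0.01 SD at the three correlations. With an assumed PHQ-9 SD of 5, that is about 0.25, 0.15 and 0.05 points, on a secondary goal with no target width. This stands as a limit on importance.

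Finally, Section 10 words its intervals by treatment group. For those, a common T1 mean gains less: 4.2% (LIFT) and 8.8% (waitlist) at r = 0.5, and 1.2% and 2.5% at r = 0.85. The between-arm interval is nonetheless implied by the Aim 2 comparison and by the stated secondary goal.

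That the stratification factors may add little precision is true, but it does not defeat including them. They are there so that the interval matches the design.

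**Conclusion.** The point holds as a modest matter of precision and interval calibration. If T1 means are free by arm, adjustment would narrow the reported between-arm interval by about 13% to 4% in the whole sample, and by about 12% to 2% for PHQ-9 in the set with scores of 5 or more. Both ranges assume r of 0.5 to 0.85, equal SDs and complete data. Missing T2 data reduces the gain. It is near zero at high r with a T2/T1 SD ratio near 1.2, and larger if scores are less spread at T2 than at T1.

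For PHQ-9, much of the narrowing corrects an interval wider than the design warrants. The true precision gain is about 2% to 6% at r = 0.5, depending on the assumed strata and set, and smaller at higher r. For the other outcomes more of the gain is real precision, though less so the more closely their baseline follows PHQ-9.

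The tempting stronger reading, that the planned comparison is biased or invalid, is not supported: both estimators are unbiased under randomisation. Every correlation, SD, dropout rate and stratum cut-point used here is an assumption.

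**What to change.** In Section 10, state that the LIFT-minus-waitlist difference and its 95% interval will be estimated with adjustment for the outcome's own baseline score, either by ANCOVA on T2 or by a mixed model with T1 means constrained equal across arms. Add the stratification factors used at randomisation: years of experience for every outcome, and baseline PHQ-9 for outcomes other than PHQ-9, whose own baseline already serves. If a common T1 mean is already intended, say so; that settles the baseline question, and only the stratification terms remain to be named.

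The cost is about two sentences and no new data. If the stratification factors prove unrelated to the outcome, the interval widens by under 1%. Naming the model in advance also removes a later choice between change-score, ANCOVA and common-T1-mean results.

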15. IRB

Duke University Health System (DUHS) IRB will be utilized as the IRB of record for this project pilot randomized, RCT and the future RCT.

16. Risk-benefit assessment

The overall study is believed to be a minimal risk trial. However, there is a potential risk for mild anxiety when answering survey questions although this has not been observed in previous similar studies to date. Participants will be informed that should they need to pause survey completion at any time, they can do so and return at a later time to complete the survey. They may also choose to not answer any questions that make them uncomfortable. The LIFT app also provides numbers for distress resources nationally and at Duke.

Additionally, as with any research, but especially one that involves technology (i.e., mobile app), there is always a potential loss of confidentiality. Appropriate safeguards are in place to ensure confidentiality, as described in the RDSP. Participants can choose not to participate and continue receiving normal standard of care.

Pro00107657: A self-directed mobile mindfulness intervention to address distress and burnout in frontline healthcare workers.

Version Date: v1.0 - 3/31/2021

NCT04816708

Adequacy of protection against risks

Recruitment and informed consent procedures

First, the Duke Institutional Review Board (IRB) will review and approve the safety and ethics of the study protocol before study initiation. Informed consent will be required from all participants. Participant enrollment is completely voluntary, as the potential participants will not be individually approached by study personnel for enrollment.

Protections against risk

General oversight

There are several ongoing mechanisms for monitoring the occurrence of adverse events. The investigators will perform day-to-day monitoring of the study. This research team has demonstrated in research involving nearly 1,500 participants to date that they can keep careful records of participants study engagement and wellbeing. Careful monitoring of all persons entering the study will minimize attrition and will ensure the clinical safety. This monitoring is facilitated by a telephone number (PI's cell phone) and email address (PI's e-mail address) provided to participants upon entry into the study to report concerns related to study participation, weekly meetings between the clinical research coordinators and co-investigators to discuss study progress and any adverse events, and direct supervision of the study by the PIs.

Plans to prevent coercion and to ensure voluntary participation

We will strive to create an environment free of any coercive practices for participants. We will stress that study involvement is absolutely voluntary and that choosing to participate or not participate will not affect their employment in any way. [name] will not be involved in any recruitment activities in the medical ICU, as he holds a clinical leadership position in that unit, so as to avoid the appearance of coercion. No nursing managers will be involved in recruitment either, also to avoid the appearance of coercion.

Vulnerable populations. We will not enroll participants from vulnerable populations (e.g., imprisoned persons, minors).

17. Data & safety monitoring

Data Accuracy and Protocol Compliance.

The PI will supervise the study, including data management, data accuracy, and protocol compliance. The PI will be the chief data manager and will adhere to established federal and institutional safety and protection guidelines. To assure data accuracy, the PI will review data system reports on a routine basis. These reports will show enrollment, missing data, and other values that are neither study ID- nor outcome-based.

Quality Assurance

First, the electronic data entry system "forces" responses to key questionnaire items (e.g., baseline demographics and surveys) before allowing progression to treatment arm randomization and access to app content, thereby minimizing missing data at timepoint 1.

Similarly forced responses are required at timepoint 2 before a participant can be noted to have completed the study. Each time the study team logs into the secure data entry system, prompts appear on the welcome screen that show what data elements remain incomplete (as well as the time frame within which they must be entered) for all site participants.

Pro00107657: A self-directed mobile mindfulness intervention to address distress and burnout in frontline healthcare workers.

Version Date: v1.0 - 3/31/2021

NCT04816708

The study PI will ensure the validity of the data system by examining electronic summary case report forms within the EDC system to ensure adequacy and accuracy of data collection as well as transcription to the database itself after enrollment of the first 5 participants. Agreement will be reviewed, and discrepancies will be discussed.

Adverse events (AEs), serious adverse events, (SAEs) and unanticipated problems (UPs).

It is recognized that there is a slight risk that some participants may experience mild anxiety when answering survey questions. This has not been experienced to date from similar studies previously performed. However, should a participant report symptoms related to increased anxiety/emotional distress, an alert will automatically be triggered via the mobile app and sent to the study team (i.e. the study manager, PI, and co-PI). When necessary, participants who experience psychological distress related to completing questionnaires will be referred for appropriate psychiatric or psychological care. In addition, phone numbers for institutional, local, and national resources for acute distress will be available in the app.

Certain questions in baseline and completion questionnaires will trigger “alert” values (e.g. suicidal ideation). For specific symptoms (such as the suicidal ideation), a delegated study team member ([name] or [name]) will call the participant and assess the severity of the situation, triaging them as appropriate to psychiatric support. For other matters, the study team will maintain frequent telephone contact with participants and can refer those with concerning symptoms as appropriate.

Since this is a psychosocial intervention, we do not expect study related physical issues to occur. Furthermore, there is no lab work involved.

It is anticipated, in this study, for AEs to be extremely rare as it is a behavioral study. However, it is possible that participants could become distressed due to the ongoing stress of work and the COVID-19 pandemic. Therefore, for this study, only increased levels of distress related to completing the questionnaires or completing the mobile mindfulness therapy will be considered AEs.

Like AEs, it is not anticipated that SAEs will occur. However, for this study, an SAE would be defined as a suicide attempt, a hospitalization, or death. All serious adverse events will be reported within the standard timelines required to the IRB as appropriate and when applicable.

It is expected that some LIFT practices will be missed by most participants. As such, these will not be considered protocol deviations. Should other protocol deviations or unanticipated problems occur, they will be discussed with the PI, documented, and reported to the IRB as appropriate and when applicable.

Period and Frequency for Event Assessment and Follow-Up

Protocol deviations and other unanticipated problems, as well as AEs and SAEs, will be recorded in the data collection system throughout the study and reported, as appropriate, to the IRB when applicable.

Pro00107657: A self-directed mobile mindfulness intervention to address distress and burnout in frontline healthcare workers.

Version Date: v1.0 - 3/31/2021

NCT04816708

The study team will record all reportable events with start dates occurring any time after informed consent is obtained until 7 (for non-serious AEs) or 30 days (for SAEs) after the last day of study participation.

Characteristics of an Adverse or Serious Adverse Event

To assess relationship of an event to study intervention, the following guidelines are used:

1. Related (Possible, Probable, Definite)
 1. The event is known to occur with the study intervention.
 2. There is a temporal relationship between the intervention and event onset.
 3. The event abates when the intervention is discontinued.
 4. The event reappears upon a re-challenge with the intervention.
2. Not Related (Unlikely, Not Related)
 1. There is no temporal relationship between the intervention and event onset.
 2. An alternate etiology has been established.

Expectedness

The Study PI will be responsible for determining whether an event is expected or unexpected. An event will be considered unexpected if the nature, severity, or frequency of the event is not consistent with the risk information previously described for the intervention.

Severity

The following scale will be used to grade adverse events:

1. Mild: no intervention required; no impact on activities of daily living (ADL)
2. Moderate: minimal, local, or non-invasive intervention indicated; moderate impact on ADL
3. Severe: significant symptoms requiring invasive intervention; subject seeks medical attention, needs major assistance with ADL

Reporting Procedures

Serious (fatal or life-threatening) SAEs that are unanticipated and that are related to the intervention will be reported to the IRB in the following manner:

(a) Immediately (within 24 hours) upon learning of an unanticipated study-related death, study personnel will notify the IRB via e-mail or fax by providing a brief summary of the event. Then, within 1 week (five business days), study personnel will send to the IRB a Safety Event submission in the eIRB.

(b) For a reportable serious adverse event, study personnel will notify the IRB within five business days of the investigator becoming aware of the event. Study personnel will send a Safety Event

Pro00107657: A self-directed mobile mindfulness intervention to address distress and burnout in frontline healthcare workers.

Version Date: v1.0 - 3/31/2021

NCT04816708

submission in the eIRB.

Protocol Deviations and Other Unanticipated Problem Reporting

Incidents or events that meet the reporting criteria, as outlined by the Duke IRB, will be reported to the Duke IRB as needed.

The following will be included, at a minimum:

- A detailed description of the event, incident, experience, or outcome.
- A description of any changes to the protocol or other corrective actions that have been taken or are proposed in response to the unanticipated problem.

Compliance regarding Adverse Event Reporting.

The study team will be required to document and report adverse events (including serious adverse events) to the Institutional Review Board (IRB), as appropriate and in line with institutional reporting criteria.

17. Data management.

All data is captured via the electronic data capture system (EDC) has been developed and is supported by programming service providers, Pattern Health. This data will be exported data will be exported from Pattern Health Servers in .CSV format, and stored in secure, Duke University-approved, password protected, cloud systems (i.e., Box). Study staff will complete electronic case report forms (eCRFs) securely integrated within the LIFT platform that includes an electronic database. Study personnel will utilize these data systems to create scheduled reports on the trials' conduct (e.g., study milestones) to enhance the study's quality. We will monitor the quality and consistency of data in a number of ways. Monthly data cleaning will be done by the study team using customized group-blinded reports that will identify missing, outlier, or nonsensical data at time points when remedying them is feasible.

18. Privacy, Data Storage & Confidentiality

Privacy

The study team will closely safeguard participant privacy regarding protected health and personal information. A study ID number will be generated at the time of consent and will be maintained in a secure file (e.g., linker file) which will contain the participant. Further, names, birth dates, telephone numbers, and addresses will be stored securely as described in the RDSP and only accessible by delegated study team members. Study participants cannot view data via the ePRO system or the electronic data capture (EDC) system, supported by Pattern Health. Participants will only have access to the ePRO system and will access the one-way view ePRO system via secure, PHI-free email or text links sent from the app.

Digital security

The study digital infrastructure consists of a mobile (i.e., native) app with a built-in electronic participant reported outcomes (ePRO) function, an electronic data capture (EDC) system, and a separate Duke University-approved, password protected, cloud systems (i.e., Box).

Pro00107657: A self-directed mobile mindfulness intervention to address distress and burnout in frontline healthcare workers.

Version Date: v1.0 - 3/31/2021

NCT04816708

- **LIFT app:** LIFT is a native app. The programming service providers, Pattern Health, endeavor to build technological solutions that preserve the privacy, confidentiality, and security of protected health information that may be part of health records or research datasets. Protected Health Information (PHI) is handled according to appropriate Health Insurance Portability and Accountability Act of 1996 (HIPAA) Privacy and Security Regulations. All staff who work with sensitive data are required to complete appropriate HIPAA training with periodic updates, complete human subjects and data privacy training, comply with site IT Security Policies, and agree to the provisions of the University Rules of Behavior and Sanction Policy. All sites strive to implement reasonable security controls in its product builds guided by FISMA, HIPAA, and OMB Circular A-130, Appendix III. Pattern Health has implemented and maintains several security protocols and controls for apps as well. Pattern Health has developed a formal information security program, with a named individual responsible for its overall execution. Pattern Health also periodically conducts an information technology (IT) security risk assessment on its projects, maintains formal documented protocols for reporting security breaches, assesses and manages security risks associated with vendors and subcontractors, maintains employee on-boarding and off-boarding policies that protect study data and integrity, and ensures continuing employee awareness of and education on security policies, standards, and procedures. In terms of development approaches to security, Pattern Health evaluates and installs security patches in a timely fashion, protects systems against self-propagating malware, maintains secure coding policies and practices, and utilizes standardized secure build processes to protect Pattern Health hardware that accesses customer networks, protecting confidential data against attack. All storage of confidential participant data on Pattern Health hardware is strictly prohibited, and the use of off-shore service providers and/or data center facilities is prohibited unless approved by client. For our study, the native app application and supporting backend system that Pattern Health develops will be hosted securely per DHTS regulations.
